myositis, Grade 1	Refer patient to rheumatologist or neurologist.								
	Initiate treatment as per institutional guidelines.								
Immune-related	Withhold atezolizumab for up to 12 weeks after event onset ^a and contact sponsor.								
myositis, Grade 2	Refer patient to rheumatologist or neurologist.								
	Initiate treatment as per institutional guidelines.								
	Consider treatment with corticosteroid equivalent to 1-2 mg/kg/day i.v. methylprednisolone and convert to 1-2 mg/kg/day oral prednisone or equivalent upon improvement.								
	If corticosteroids are initiated and event does not improve within 48 hours after initiating corticosteroids, consider adding an immunosuppressive agent.								
	If event resolves to Grade 1 or better, resume atezolizumab. b								
	If event does not resolve to Grade 1 or better while withholding atezolizumab, permanently discontinue atezolizumab and contact sponsor. c								
Immune-related	Withhold atezolizumab for up to 1 weeks after event onset ^a and contact sponsor.								
myositis, Grade 3	Refer patient to rheumatologist or neurologist.								
	Initiate treatment as per institutional guidelines.								
	Respiratory support may be required in more severe cases.								
	Initiate treatment with corticosteroids equivalent to 1-2 mg/kg/day i.v. methylprednisolone or higher-dose bolus if patient is severely compromised (e.g. cardiac or respiratory symptoms, dysphagia, or weakness that severely limits mobility); convert to 1-2 mg/kg/day oral prednisolone or equivalent upon improvement.								
	If event does not improve within 48 hours after initiating corticosteroids, consider adding an immunosuppressive agent.								
	If event resolves to Grade 1 or better, resume atezolizumab. ^b								
	If event does not resolve to Grade 1 or better while withholding atezolizumab, permanently discontinue atezolizumab and contact sponsor. c								
	For recurrent events, treat as a Grade 4 event.								
Immune-related	Permanently discontinue atezolizumab and contact sponsor. c								
myositis, Grade 4	Refer patient to rheumatologist or neurologist.								
	Initiate treatment as per institutional guidelines. Respiratory support may be required in more severe cases.								
	Initiate treatment with corticosteroids equivalent to 1-2 mg/kg/day i.v. methylprednisolone or higher-dose bolus if patient is severely compromised (e.g. cardiac or respiratory symptoms, dysphagia, or weakness that severely limiting mobility); convert to 1-2 mg/kg/day oral prednisone or equivalent upon improvement.								
	If event does not improve within 48 hours after initiating corticosteroids, consider adding an immunosuppressive agent.								

23 MAY 2023 Version 6.0 Page: 79 of 181

Table 7–13: Management guidelines for immune-related myositis

Event	Management
	If event resolves to Grade 1 or better, taper corticosteroids over ≥ 1 month.

i.v. = intravenous

- a: Atezolizumab may be withheld for a longer period of time (i.e., > 12 weeks after event onset) to allow for corticosteroids (if initiated) to be reduced to ≤ 10 mg/day oral prednisone or equivalent. The acceptable length of the extended period of time must be agreed upon by the investigator and the sponsor.
- b: If corticosteroids have been initiated, they must be tapered over ≥ 1 month to ≤ 10 mg/day oral prednisone or equivalent before atezolizumab can be resumed.
- c: Resumption of atezolizumab may be considered in patients who are deriving benefit and have fully recovered from the immune-related event. Patients can be re-challenged with atezolizumab only after approval has been documented by both the investigator (or an appropriate delegate) and the sponsor.

Systemic immune activation

Systemic immune activation (SIA) is a rare condition characterized by an excessive immune response. Given the mechanism of action of atezolizumab, SIA is considered a potential risk when given in combination with other immunomodulating agents. SIA should be included in the differential diagnosis for patients who, in absence of an alternate etiology, develop a sepsis-like syndrome after administration of atezolizumab.

Recommendations regarding early identification of SIA are provided below. In event of suspected SIA, the sponsor should be contacted immediately for additional guidance and study treatment should be interrupted. At ezolizumab should be permanently discontinued in patients with life-threatening immune-mediated adverse events.

Early disease recognition is critical, and the clinician should consider SIA if, in absence of alternative etiologies, ≥ 2 of the following are present:

- Hypotension refractory to aggressive i.v. fluid challenge. May/can require vasopressin support
- Respiratory distress requiring aggressive supportive care. Supplemental oxygen, possible intubation.
- Fever greater than 38.5°C
- Acute renal or hepatic failure
- Bleeding from coagulopathy
- Unexplained laboratory abnormalities (change from baseline):
- Cytopenia (≥ Grade 2 in two or more lineage), significant transaminitis, coagulopathy, elevated creatinine.

Initial evaluation should include CBC with peripheral smear, PT, PTT, fibrinogen, D-dimer, ferritin, triglyceride, AST/ALT, total bilirubin, LDH, and a complete neurologic and abdominal examination (assess for hepatosplenomegaly).

23 MAY 2023 Version 6.0 Page: 80 of 181

If cytopenia (≥ 2 lineages and change from baseline) are present or ferritin is ≥ 3000 ng/mL, the following evaluations should also be performed:

- Bone marrow biopsy/aspirate (assess for evidence of hemophagocytosis)
- sCD25 (soluble IL-2 receptor)
- Natural killer cell activity
- Cytomegalovirus, Epstein-Barr virus and herpes-simplex virus evaluation (evaluate for reactivated or active disease)

SIA is a clinical syndrome characterized by the following:

- Onset greater than 24 hours after exposure to drug, and
- Progressive clinical deterioration in an acutely ill patient (in absence of an alternate etiology), *and*
- Involving multiple organs (≥ 2), and
- Demonstrating specific laboratory abnormalities.

Diagnosis of SIA should only be made in patients who present with a constellation of clinical findings as outlined above and who fulfill the following established diagnostic criteria in the absence of an alternate etiology.

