6.4.1.3 Withdrawal criteria

Patients *must* be withdrawn from the study treatment if any of the following occurs:

• Consent withdrawal at their own request or at the request of their legally acceptable

23 MAY 2023 Version 6.0 Page: 48 of 181

representative.

o At any time during the study and without giving reasons, a patient may decline to participate further. The patient will not suffer any disadvantage as a result.

• Substantial non-compliance with study procedures

- Patients requiring a dose interruption of rogaratinib due to toxicity > 21 days from the next intended dose or due to other reasons for > 31 days from the next intended dose will be withdrawn from the study treatment.
- o Off study drug (atezolizumab) longer than 42 days from the next intended dose
 - If, in the judgment of the investigator, the patient is likely to derive clinical benefit from resuming atezolizumab after a hold > 42 days, atezolizumab may be restarted after sponsor approval.
 - If patients must be tapered off steroids used to treat adverse events, atezolizumab may be held for > 42 days. The acceptable length of interruption will depend on agreement between the investigator and the sponsor. (See also Section 7.4.3.3 for further details and specific recommendations).
- Lost to follow-up
- o Use of another non-protocol anti-cancer therapy

• Unacceptable toxicity

- If, in the investigator's opinion, continuation of study would be harmful to the patient's well-being.
- Any toxicity requiring rogaratinib dose reductions below dose level -2.
- Any toxicity requiring rogaratinib dose interruption longer than 21 days to resolve to Grade 1 or better.
- Severe (Grade 3 or higher) allergic reactions such as exfoliative erythroderma, anaphylaxis, or vascular collapse.
- o Severe (Grade 3 or higher) infusion-related reactions.
- Any other potential adverse reaction deemed sufficiently serious to warrant discontinuation of treatment by the investigator or his designated associate(s).

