- O Any decrease in visual acuity, ocular pain or discomfort, or symptomatic retinal disorders including retinal detachment / retinal pigment epithelial detachment / central serous retinopathy / retinal vein occlusion classified analog to CTCAE v.4.03 as Grade 2 or higher. Based on the individual benefit risk assessment and after discussion with the sponsor, patient may interrupt treatment until recovery to at least Grade 1 and then treatment may be resumed at one dose level below. Patients with low visual acuity at baseline (best corrected visual acuity worse than 20/40 and up to 20/200) have to undergo individual clinical evaluation to determine the maintenance in the study, according to investigator's judgement and based on the individual benefit risk

23 MAY 2023 Version 6.0 Page: 49 of 181

assessment.

- o Liver toxicity with AST or ALT > 3 x ULN with concomitant bilirubin > 2 x ULN in the absence of an alternative explanation for these elevations.
- \circ \geq Grade 3 liver toxicity with ALT or AST > 5 x ULN and/or total bilirubin > 3 x ULN in the absence of an alternative explanation for these elevations.
- Any grade myasthenic syndrome/myasthenia gravis, Guillain-Barré or meningoencephalitis.
- o Any grade of recurrent symptomatic pancreatitis.
- o Newly diagnosed soft tissue mineralization suspected to be caused by rogaratinib.
- o Grade 4 non-hematological toxicity (laboratory abnormalities of any grade will not be considered toxicity unless deemed clinically significant by the investigator).
- o Grade 3 or higher non hematologic toxicity atezolizumab-related and requiring treatment discontinuation (see also Section 7.4.3.3).
- Any Grade 2 or higher non hematologic toxicity atezolizumab-related not resolving at Grade 1 or better within 12 weeks despite symptomatic therapy
- Pregnancy as confirmed by a positive serum beta-HCG test. Pregnancy will be reported under the same timelines as a serious adverse event.
- At specific request of the sponsor.

Patients may be withdrawn from the study treatment if any of the following occurs:

- If the patient develops conditions which would have prevented his/her entry into the study according to the inclusion / exclusion criteria, he/she must be withdrawn immediately if safety is concerned; in other cases, the investigator will decide whether there is a conflict for the patient to continue.

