7.4.3.3 Dose modifications of atezolizumab

There will be no dose reduction for atezolizumab in this study.

Patients may temporarily suspend study treatment if they experience toxicity that is considered related to study drug and requires a dose to be held.

If atezolizumab is held because of related adverse events for > 42 days beyond the next scheduled dosing, the patient will be discontinued from atezolizumab and will be followed for safety and efficacy as specified in Section 9.2.3.

If, in the judgment of the investigator, the patient is likely to derive clinical benefit from resuming atezolizumab after a hold > 42 days, atezolizumab may be restarted with the approval of the sponsor.

If patients must be tapered off steroids used to treat adverse events, atezolizumab may be held for > 42 days. The acceptable length of interruption will depend on agreement between the investigator and the sponsor. During steroid taper and if toxicity has resolved to Grade ≤ 1 , rogaratinib may continue as monotherapy.

23 MAY 2023 Version 6.0 Page: 63 of 181

Infusion-related reactions

Severe infusion reactions have occurred in patients in clinical trials of atezolizumab. Refer to the latest available version of atezolizumab IB for further details. Immediately interrupt infusion in patients with mild or moderate infusion-related reactions (Grade 1 and 2). Permanently discontinue atezolizumab in patients with Grade 3 or 4 infusion-related reactions.

The management of infusion-related reactions will be according to severity as follows:

In the event that a patient experiences a mild (NCI CTCAE Grade 1) infusion-related event, the infusion rate should be immediately interrupted at the time of event onset. Once the event has resolved, the investigator should wait for 30 minutes and then restart the infusion at half the rate been given at time of event onset. If tolerated at the reduced rate for 30 minutes, the infusion rate may then be increased to the original rate. If the symptoms recur, discontinue infusion of this dose.

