	Re-evaluate on serial imaging	Refer patient to pulmonary and infectious disease specialist and consider	Oral or i.v. broad-spectrum
	Consider patient referral to pulmonary specialist	bronchoscopy or BAL with or without transbronchial biopsy	administered in parallel to the immunosuppressive treatment
	For recurrent events, treat as a Grade 3 or 4 event	Initiate treatment with 1–2 mg/kg/day oral prednisone or equivalent	Bronchoscopy or BAL with or without transbronchial biopsy is recommended
		Resume atezolizumab if event resolves to ≤ Grade 1 within 12 weeks	Initiate treatment with 1–2 mg/kg/day i.v. methylprednisone
		Permanently discontinue atezolizumab if event does not resolve to ≤ Grade 1 within 12 weeks and contact the sponsor ^{a, b, c, d}	If event does not improve within 48 hours after initiating corticosteroids, consider adding an immunosuppressive agent
		For recurrent events or events with no improvement after 48–72 hours of corticosteroids, treat as a Grade 3 or 4 event	If event resolves to Grade 1 or better, taper corticosteroids over ≥ 1 month

BAL = bronchoscopic alveolar lavage; CTCAE = Common Terminology Criteria for Adverse Events; i.v. = intravenous.

a: If corticosteroids have been initiated, they must be tapered over ≥ 1 month to ≤ 10 mg/day oral prednisone or equivalent before atezolizumab can be resumed.

b: Atezolizumab may be withheld for a period of time beyond 12 weeks to allow for corticosteroids to be reduced to ≤ 10 mg/day oral prednisone or equivalent. The acceptable length of the extended period of time must be agreed upon by the investigator and the sponsor.

c: Resumption of atezolizumab may be considered in patients who are deriving benefit and have fully recovered from the immune-related event. Patients can be rechallenged with atezolizumab only after approval has been documented by both the investigator (or an appropriate delegate) and the sponsor.

d: In case of pneumonitis, atezolizumab should not be resumed after permanent discontinuation.

23 MAY 2023 Version 6.0 Page: 67 of 181

Immune-mediated hepatitis

Immune-mediated hepatitis, defined as requiring use of corticosteroids and with no clear alternate etiology, occurred in patients receiving atezolizumab treatment. Liver test abnormalities occurred in patients who received atezolizumab. Refer to the latest available version of atezolizumab IB for further details. For management of liver toxicity, refer to the Section 7.4.3.2.2 and Table 7–5.

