of treatment and documented by the investigator. The sponsor is available to advise as needed.

b If corticosteroids have been initiated, they must be tapered over ≥1 month to the equivalent of ≤10 mg/day oral prednisone before atezolizumab can be resumed.

c Resumption of atezolizumab may be considered in patients who are deriving benefit and have fully recovered from the immune-mediated event. The decision to rechallenge patients with atezolizumab should be based on the investigator's benefit-risk assessment and documented by the investigator. The sponsor is available to advise as needed.

23 MAY 2023 Version 6.0 Page: 74 of 181

Infections

Severe infections, including sepsis, herpes encephalitis, and mycobacterial infection leading to retroperitoneal hemorrhage occurred in patients receiving atezolizumab. Monitor patients for signs and symptoms of infection and treat with antibiotics for suspected or confirmed bacterial infections. Withhold atezolizumab for \geq Grade 3 infection.

Pancreatitis

Symptomatic pancreatitis without an alternative etiology occurred in clinical trials of atezolizumab. Monitor patients for signs and symptoms of acute pancreatitis.

The differential diagnosis of acute abdominal pain should include pancreatitis. Appropriate work-up should include an evaluation for ductal obstruction, as well as serum amylases and lipase tests.

See Table 7–10 for management guidelines for pancreatic events, including pancreatitis.

Table 7-10: Management guidelines for pancreatic events, including pancreatitis

Event	Management					
Amylase and/or lipase	Continue atezolizumab.					
elevation, Grade 2 1.5–2.0×ULN	Monitor amylase and lipase weekly.					
	For prolonged elevation (e.g., $>$ 3 weeks), consider treatment with 10 mg/day oral prednisone or equivalent.					
Amylase and/or lipase	Withhold atezolizumab.					
elevation, Grade 2 >2.0-5.0 × ULN,	Refer patient to gastrointestinal specialist.					
Grade 3 or 4	Monitor amylase and lipase every other day.					
	If no improvement, consider treatment with 1−2 mg/kg/day oral prednisone or equivalent.					
	Resume atezolizumab if event resolves to Grade 1 or better within 12 weeks. a, b					
	Permanently discontinue atezolizumab and contact sponsor if event does not resolve to Grade 1 or better within 12 weeks. a, b, c					
	For recurrent events, permanently discontinue atezolizumab and contact sponsor					
Immune-related	Withhold atezolizumab.					

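### Atezolizumab holds: the general sections default to discontinuation after 42 days unless an exception applies, while the event tables direct resumption on recovery within 12 weeks without naming sponsor approval

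*Protocol*

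**What the plan says.** **General rule.** The rule at the opening of Protocol Section 7.4.3.3 begins "If atezolizumab is held because of related adverse events for > 42 days beyond the next scheduled dosing" and takes such a patient off atezolizumab. Section 6.4.1.3 lists, among the reasons for mandatory withdrawal from study treatment, "Off study drug (atezolizumab) longer than 42 days from the next intended dose".

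**Exceptions.** Both sections attach the same two.
- If the investigator expects clinical benefit from "resuming atezolizumab after a hold > 42 days, atezolizumab may be restarted with the approval of the sponsor" (Section 7.4.3.3). Section 6.4.1.3 matches: "resuming atezolizumab after a hold > 42 days, atezolizumab may be restarted after sponsor approval".
- A hold may exceed 42 days while steroids are tapered, for a length agreed between investigator and sponsor.

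**Event tables.** These use 12 weeks.
- Table 7-6 (Grade 2 pulmonary): "Resume atezolizumab if event resolves to ≤ Grade 1 within 12 weeks". Table 7-7 is similar.
- Table 7-10 (pancreatic): "Resume atezolizumab if event resolves to Grade 1 or better within 12 weeks". The adrenal row of Table 7-8 is similar.
- The hypophysitis rows of Table 7-8, Table 7-9 (Grade 2 neuropathy), Table 7-12 (Grade 2 renal) and Table 7-13 (Grade 2 myositis) allow withholding for up to 12 weeks from event onset, then resumption on recovery. Facial paresis requires full resolution.
- Table 7-5 (Grade 2 hepatic, beyond 5 days) restarts on recovery and discontinues if there is none within 12 weeks.

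**Other statements.** Section 6.4.1.3 also withdraws patients for Grade 2 or higher atezolizumab-related non-hematologic toxicity "not resolving at Grade 1 or better within 12 weeks despite symptomatic therapy". Within Section 7.4.3.3, the sentence after the list of reasons to withhold allows resumption on recovery to Grade 0–1, with neither a time limit nor an approval step.

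**The concern.** Take a patient whose event resolves after the 42-day limit but inside 12 weeks. Under the general rule the patient is off atezolizumab unless the sponsor approves a restart or a taper explains the hold. Under the event table the site resumes on recovery. A site that works from the table could re-expose a patient after immune-mediated toxicity without the sponsor review that two sections require. Another site could withdraw a similar patient.

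The section consulted may also decide whether rogaratinib continues. These choices feed descriptive outputs: reasons for discontinuing treatment (Protocol 10.3.1, SAP 6.1.1), duration of treatment (SAP 6.4), and the treatment-emergent window, which is counted from the last dose of each drug (SAP 6.4.2).

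**Working it through.** The plan states no figure to reproduce. The check puts both limits on one clock and then compares the rules.

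**1. Timing**

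Inputs:
- Dosing interval: 21 days (Section 7.4.1.2).
- General limit: 42 days past the next scheduled dose (Sections 6.4.1.3 and 7.4.3.3).
- Table limit: 12 weeks = 12 × 7 = 84 days.

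Let onset be x days after the last infusion, with 0 ≤ x ≤ 21, and let atezolizumab be held from the next scheduled dose.
- General limit, in days after onset: L = (21 − x) + 42 = 63 − x.
- Window between the limits, if the 12 weeks run from onset: W = 84 − L = 21 + x.

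| x | L (days after onset) | W (days) |
|---|---|---|
| 0 | 63 | 21 |
| 7 | 56 | 28 |
| 14 | 49 | 35 |
| 21 | 42 | 42 |

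The window is 21 to 42 days. Only some rows state that the clock starts at onset. Tables 7-5, 7-6, 7-7, 7-10 and the adrenal row of 7-8 give no start point. If their 12 weeks were counted from the missed dose (an assumption), the window would be 84 − 42 = 42 days whatever the onset day.

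**2. What applies inside the window**

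| | Sections 6.4.1.3 and 7.4.3.3 | Event tables |
|---|---|---|
| Default | Discontinue | Resume on recovery |
| Sponsor approval to resume | Required after 42 days | Not named for recovery within 12 weeks |
| Sponsor agreement on a taper extension | Once the hold passes 42 days | In most footnotes, only beyond 12 weeks |
| Clock | Next scheduled dose | Event onset, or not stated |

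The tables tie sponsor involvement mainly to non-recovery, rechallenge or extension past 12 weeks. The Grade 2 myositis row asks the site to contact the sponsor when withholding, but contact is not approval.

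**3. Which events the taper exception leaves out**

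Steroids are directed for Grade 2 hepatic events beyond 5 days, Grade 2 pulmonary events, Grade 2 colitis that persists or recurs, Grade 3 colitis, hypophysitis, adrenal insufficiency, Grade 2–3 pancreatitis, Grade 2 renal events and Grade 3 myositis. They are optional or left to local practice for:
- amylase/lipase elevation (considered if there is no improvement);
- Grade 2 neuropathy (institutional guidelines);
- Grade 2 myositis (to be considered).

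**4. Two further differences**

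- *Scope.* Study treatment means both drugs (Definitions of terms; Section 7.2), so Section 6.4.1.3 ends both. Section 7.4.3.3 names atezolizumab only. It mentions rogaratinib monotherapy during a steroid taper, yet it sends the discontinued patient to the follow-up procedures of Section 9.2.3.
- *Taper extension.* Section 7.4.3.3 requires investigator–sponsor agreement, both in its opening and in its general management text. Footnote a of Table 7-9 leaves the length to the investigator's documented benefit-risk assessment, with the sponsor available for advice.

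**The case against.** A reader might infer that atezolizumab must stop outright at 42 days and that the tables order the opposite. The documents do not support that. Both sections follow the 42-day rule directly with two exceptions, so it is a default with an approval route. Most table events call for steroids and so fall under the taper exception. A site can also satisfy both rules by obtaining approval before resuming. The tables sit inside Section 7.4.3.3, and their silence need not waive the rule that opens it.

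The limits also do not always measure the same thing. The 42 days count time off drug, while several rows, and the 12-week item in Section 6.4.1.3, count time to resolution. Carrying both triggers in Section 6.4.1.3 is not in itself a contradiction. The enzyme example is imperfect too, since an elevation lasting past six weeks may well be on steroids by then.

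Finally, the statistical consequences are slight. DLTs are assessed in Cycle 1, before any such hold could accrue, and no further analysis is planned after primary completion (Section 5.2.3).

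These points stand, and they narrow the concern. They do not remove it. Nothing tells a site that the general approval rule overrides the table. The taper exception does not reach a patient who is not on steroids. The differences in scope and in the taper agreement remain under any reading of the limits.

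**Conclusion.** The concern holds in limited form. The general sections and the event tables set different defaults and different approval requirements for a patient who recovers between the two limits, and no text sets precedence. The conflict matters mainly for amylase/lipase elevation, Grade 2 neuropathy and Grade 2 myositis.

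The window is 21 to 42 days if the 12 weeks run from onset. That start point is stated in some rows and assumed for the others. The documents do not give the number of patients who would fall in the window.

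The differences over one drug or both, and over who agrees a longer taper, are real and come from the same passages. What is at stake is consistent handling of re-exposure after immune toxicity, sponsor oversight and whether rogaratinib continues. No sample size, DLT decision or stated statistical figure is affected.

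**What to change.** Reconcile the following: both items in Section 6.4.1.3; Table 7-5; the opening of Section 7.4.3.3 and its sentence on resuming after recovery; the general text on extending holds; and Tables 7-6 to 7-10, 7-12 and 7-13 with their footnotes. The text should state:

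1. which limit prevails, or how the general and event-specific limits fit together;
2. when each clock starts, and whether it counts time off drug or time to resolution;
3. when sponsor approval or agreement is needed, including for a taper extension;
4. whether one or both drugs stop.

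Event-specific limits can stay if their relation to the general rule is stated. In the same pass, check the Grade 3 myositis row of Table 7-13, which reads as a hold of up to 1 week while its footnote speaks of going beyond 12 weeks. Which clinical rule applies is for the sponsor to decide.

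The cost is protocol wording only, with no new data and no change to the planned analyses.

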In the event that a patient experiences a moderate infusion-related event (NCI CTCAE Grade 2) or flushing, fever, or throat pain, the patient should have his or her infusion immediately interrupted and should receive aggressive symptomatic treatment (e.g. oral or i.v. antihistamine, anti-pyretic, glucocorticoids, epinephrine, bronchodilators, oxygen). The infusion should be restarted only after the symptoms have adequately resolved to baseline grade. The infusion rate at restart should be half of the infusion rate that was in progress at the time of the onset of the infusion-related event. For the subsequent infusion, administer oral premedication with antihistamine and anti-pyretic and monitor closely for infusion-related reactions.

For severe or life-threatening infusion-related events (NCI CTCAE Grade 3 or 4), the infusion should be stopped immediately, and aggressive resuscitation and supportive measures should be initiated (administer aggressive symptomatic treatment e.g. oral or i.v. antihistamine, antipyretic, glucocorticoids, epinephrine, bronchodilators, oxygen). Patients experiencing severe or life-threatening infusion-related events will not receive further infusion and will be further managed as clinically indicated until the event resolves.

As per the IB withhold atezolizumab for any of the following:

- Grade 2 pneumonitis
- Aspartate aminotransferase (AST) or alanine aminotransferase (ALT) greater than 3 and up to 5 times upper limit of normal (ULN) or total bilirubin greater than 1.5 and up to 3 times ULN
- Grade 2 or 3 diarrhea or colitis
- Grade 2 or 3 hypophysitis
- Symptomatic adrenal insufficiency,
- Grade 3 or 4 hypothyroidism or hyperthyroidism

23 MAY 2023 Version 6.0 Page: 64 of 181

- Grade 3 or 4 hyperglycemia
- Suspected Stevens-Johnson syndrome (SJS) or toxic epidermal necrolysis (TEN)
- Grade 2 immune-mediated neuropathy, including facial paresis
- Grade 2 ocular inflammatory toxicity
- Grade 2 or 3 pancreatitis, or Grade 3 or 4 increases in amylase or lipase levels (greater than 2.0 times ULN)
- Grade 3 or 4 infection
- Grade 2 infusion-related reactions
- Grade 3 rash
- Grade 1 immune-mediated pericarditis
- Grade 2 immune-related nephritis
- Grade 2 or 3 immune-related myositis

Atezolizumab may be resumed in patients whose adverse reactions recover to Grade 0–1 (except for Grade 1 immune-mediated pericarditis).

Permanently discontinue atezolizumab for any of the following:

- Grade 3 or 4 pneumonitis

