Immune-mediated	Withhold atezolizumab for up to 12 weeks after event onset. ^a						
neuropathy, including facial paresis, Grade 2	Investigate etiology and refer patient to neurologist.						
	Initiate treatment as per institutional guidelines.						
	For general immune-mediated neuropathy:						
	If event resolves to Grade 1 or better, resume atezolizumab. ^b						
	If event does not resolve to Grade 1 or better while withholding atezolizumab, permanently discontinue atezolizumab and contact the sponsor. c						
	For facial paresis:						
	If event resolves fully, resume atezolizumab ^b						
	If event does not resolve fully while withholding at ezolizumab, permanently discontinue at ezolizumab and contact the sponsor. $^{\rm c}$						
Immune-mediated	Permanently discontinue atezolizumab and contact the sponsor. ^c						
neuropathy, including facial paresis, Grade 3	Refer patient to neurologist.						
or 4	Initiate treatment as per institutional guidelines.						
Myasthenia gravis and	Permanently discontinue atezolizumab and contact the sponsor.						
Guillain-Barré syndrome (any grade)	Refer patient to neurologist.						
symatomo (arry grado)	Initiate treatment as per institutional guidelines.						
	Consider initiation of corticosteroids equivalent to 1–2 mg/kg/day oral or i.v. prednisone.						
Immune-mediated	Continue atezolizumab unless symptoms worsen or do not improve.						
myelitis, Grade 1	Investigate etiology and refer patient to a neurologist.						
Immune-mediated	Permanently discontinue atezolizumab and contact the sponsor.						
myelitis, Grade 2	Investigate etiology and refer patient to a neurologist.						
	Rule out infection.						
	Initiate treatment with corticosteroids equivalent to 1–2 mg/kg/day oral prednisone.						
Immune-mediated	Permanently discontinue atezolizumab and contact the sponsor						
myelitis, Grade 3 or 4	Refer patient to a neurologist.						
	Initiate treatment as per institutional guidelines.						

a Atezolizumab may be withheld for a longer time (i.e., >12 weeks after event onset) to allow for corticosteroids (if initiated) to be reduced to the equivalent of ≤10 mg/day oral prednisone. The acceptable length of the extended time must be based on the investigator's benefit-risk assessment and in alignment with the protocol requirement for duration of treatment and documented by the investigator. The sponsor is available to advise as needed

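### Section 7.4.3.3 permits atezolizumab to resume at residual Grade 1 facial paresis, Table 7-9 requires full resolution, and no text says which governs

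*Protocol*

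**What the plan says.** Protocol Section 7.4.3.3 gives two rules for restarting atezolizumab after facial paresis.

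The first is general. The list of reasons to withhold includes "Grade 2 immune-mediated neuropathy, including facial paresis". The sentence that closes the list reads "Atezolizumab may be resumed in patients whose adverse reactions recover to Grade" 0–1, followed by a parenthesis that excepts Grade 1 immune-mediated pericarditis and nothing else.

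The second is in Table 7-9, on neurologic disorders. Its Grade 2 row opens with "Withhold atezolizumab for up to 12 weeks after event onset" and then divides. For general immune-mediated neuropathy the instruction is "If event resolves to Grade 1 or better, resume atezolizumab". For facial paresis it is "If event resolves fully, resume atezolizumab". "If event does not resolve fully while withholding" atezolizumab, the drug is stopped permanently and the sponsor is contacted. Footnote a extends the period: "Atezolizumab may be withheld for a longer time (i.e., >12 weeks after event onset) to allow for corticosteroids" to be brought down. Footnote c leaves a way back: "Resumption of atezolizumab may be considered in patients who are deriving benefit and have fully recovered from the immune-mediated event". The Grade 1 row sends any cranial nerve disorder, facial paresis among them, to the Grade 2 guidance.

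**The concern.** The table deliberately treats facial paresis differently from other neuropathy. The general sentence does not, although the list it closes names facial paresis. That sentence also has its own exception clause with a single entry, so a reader can fairly take facial paresis to be covered by the Grade 0–1 rule. An investigator who relies on it could give atezolizumab to a patient with residual facial paresis whom the table keeps off the drug.

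The amendment history in Section 15.5 shows that facial paresis entered Version 6.0 as a newly identified risk of atezolizumab, with its own management guidance. At stake is whether that guidance is applied as the sponsor intended.

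**Working it through.** There is no figure in the plan to reproduce. The check sets the two rules side by side and then looks for anything else in the protocol that would prevent the early restart.

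| State of the patient | Withhold list and closing sentence | Table 7-9 |
|---|---|---|
| Facial paresis at Grade 2 | Withhold | Withhold |
| Improved to Grade 1 during the hold | Resumption permitted | Keep withholding |
| Still Grade 1 when the hold ends | Resumption permitted | Stop permanently |
| Fully resolved | Resumption permitted | Resume |
| New event at Grade 1 | Not listed | Manage as Grade 2, so withhold |

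The rules differ in the second and third rows. Residual Grade 1 cannot be read as full resolution. The Grade 2 row uses Grade 1 or better as the contrasting test for general neuropathy, and the Grade 1 row still treats facial paresis as an event that needs action. The last row is a gap, not a contradiction, because the list is silent on Grade 1.

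Possible safeguards elsewhere:

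- **Order of precedence.** The paragraph on motor and sensory neuropathy in Section 7.4.3.3 points to Table 7-9. Neither it nor any other text says that the table overrides the general sentence.
- **Withdrawal criteria, Section 6.4.1.3.** The criterion for atezolizumab-related non-hematologic toxicity of Grade 2 or higher requires withdrawal only if the event has not reached Grade 1 or better within 12 weeks. Residual Grade 1 facial paresis passes it.
- **The 42-day rule, Sections 6.4.1.3 and 7.4.3.3.** A hold of more than 42 days past the next scheduled dose ends atezolizumab unless the sponsor approves a restart; for a steroid taper, the length of a longer hold is agreed with the sponsor. With 21-day cycles on schedule, the next dose falls 0 to 21 days after onset. The limit is therefore reached between 0 + 42 = 42 and 21 + 42 = 63 days after onset, before the table's 12 × 7 = 84 days. Beyond that point the investigator cannot restart alone. Before it, the rule does not prevent resumption at Grade 1.
- **Steroid taper, Section 7.4.3.3.** A taper of at least one month must come before any restart, but only if corticosteroids were started. For Grade 2 neuropathy, Table 7-9 leaves treatment to institutional guidelines.

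None of these prevents an early restart at Grade 1.

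**The case against.** The strongest reply is that this is an ordinary summary followed by a specific rule. The general sentence says only that dosing may resume, so an investigator who follows Table 7-9 breaches neither text. The table is in the same section, readers are directed to it, and it has instructions written for facial paresis. The section also asks for an individual benefit-risk judgement before further dosing. The general sentence cannot be read alone for other events either: Table 7-8 restarts after Grade 3 thyroid events once symptoms are controlled and function is improving, and after Grade 3 or 4 hyperglycemia once symptoms resolve and glucose is stable. Neither test is stated as Grade 0–1.

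Much of this stands. A reader might infer that the protocol gives instructions that cannot both be obeyed. It does not: the stricter course satisfies both. What the reply does not remove is the permission. The list names facial paresis, its closing sentence states its exceptions, and facial paresis is not among them. Reading the table as controlling is sensible, but the protocol leaves that to inference. The benefit-risk judgement sets no threshold, so it does not settle whether Grade 1 is enough.

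**Conclusion.** The inconsistency is real in the current text and is limited to residual facial paresis. One rule permits a restart at Grade 1; the other requires full resolution and, failing that, permanent discontinuation. The conclusion rests on reading full resolution as excluding Grade 1, which the table's own contrast supports.

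The effect is on the safety of patients still receiving atezolizumab. Their number is not stated, nor is the expected frequency of facial paresis or its time to Grade 1, so the number of patients affected cannot be estimated. No planned analysis changes: Section 5.2.3 says that none is planned after primary completion, and the log for Amendment 3 (Section 15.3) refers to a primary completion data cut of July 2021, before the facial paresis guidance was added in 2023.

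A reader might want to size the problem in infusions, as 84 / 21 = 4 within the 12-week window. The documents do not support that as a bound. If resolution is incomplete, Table 7-9 bars dosing beyond 12 weeks too, and how early the general sentence would permit dosing depends on an unstated recovery time.

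This is a minor consistency defect, worth correcting because the sponsor has already chosen the stricter rule.

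**What to change.** Change the parenthesis that closes the withhold list to: *(except for Grade 1 immune-mediated pericarditis, and facial paresis, which must resolve fully; see Table 7-9)*.

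Optionally, to match the Grade 1 row of Table 7-9, add to the withhold list: *Grade 1 cranial nerve disorder, including facial paresis (manage as Grade 2; see Table 7-9)*. Check this against the investigator's brochure first, because the list is introduced as following it.

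A general precedence sentence is not advisable. If the tables prevailed, hepatic withholding could loosen: Table 7-5 makes no change for Grade 2 hepatic events unless they last more than 5 days, while the list withholds at once. If the stricter rule always prevailed, it could alter the thyroid and hyperglycemia restart rules and set the 42-day limit over the 12-week windows in the tables.

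The cost is one short edit, or two with the optional entry. Either needs a protocol amendment, and Amendment 5 was classed as substantial, so the change is best carried in the next amendment. That amendment made a comparable consistency edit to the same list for pericarditis.
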